9.2. Subject Exclusion Criteria

Subjects who meet any of the following criteria will not be eligible to participate in the study:

1. Has the presence or history of a clinically significant disorder involving the cardiovascular, respiratory, renal, gastrointestinal, immunologic, hematologic, endocrine, or nervous system(s) or psychiatric disease that would contraindicate participation, as determined by the Investigator.
2. Has any clinical laboratory test result outside the accepted range that has been confirmed upon re-examination and deemed to be clinically significant.
3. Has a clinically significant illness or condition any time before dosing with study drug that would contraindicate participation, as determined by the Investigator.
4. Has a life expectancy <8 weeks.
5. For age groups A and B: Has a malabsorption, gastroenterologic, or abdominal condition that would interfere with the absorption of study drug.
6. Has evidence of increased intracranial pressure.
7. Has a respiratory condition requiring intubation or resulting in active bronchiolitis, asthma, stridor, or difficulty breathing due to congestion and increased nasal secretions, including O₂ saturation \leq 92%.
8. Has a history of seizures.
9. Subject (and/or mother if subject is nursing) has used medications with actions characteristic of monoamine oxidase inhibitors (MAOIs) within 14 days before the start of the study drug is prohibited. Standard daily pediatric multivitamins may be taken until enrollment into the study but will be restricted during the study.
10. Subject (and/or mother if subject is nursing) has received preoperative opioids for more than 72 consecutive hours.
11. Subject (and/or mother if subject is nursing) has received oxycodone or oxymorphone within 48 hours prior to screening.
12. Subject (and/or mother if subject is nursing) has ingested caffeine- or xanthine-containing products (eg, theophylline) within 48 prior to screening. These products are also prohibited during periods when blood samples are collected.
13. Has a history of relevant drug allergies, food allergies, or both (ie, allergy to oxymorphone or other opioid analgesics) that could interfere with the study.
14. Parent or legal guardian is unable to provide consent for any reason (eg, mental or physical disabilities, language barriers, or is unavailable).
15. Subject (and/or mother if subject is nursing) has participated in a clinical study of an unapproved drug within the previous 30 days.
16. Is not suitable for entry into the study in the opinion of the Investigator.

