
9. For Groups A and B: Subjects are showing signs of tolerating oral intake, following surgery according to the SOC at each institution. All infants and children should be able to demonstrate strong suck and swallow reflexes and neurologic alertness and stability sufficient to handle oral secretions.
 
Prior to Administration of Oxymorphone HCl Oral Solution
 
10. For Groups A and B: Has demonstrated the ability to tolerate clear liquids, following surgery according to the SOC at each institution. All infants and children should be able to demonstrate strong suck and swallow reflexes and neurologic alertness and stability sufficient to handle oral secretions. The ability to tolerate small amounts (1 to 2 oz.) of clear liquids without emesis (over 30 to 60 minutes) would support readiness for study participation and oral intake once the physician has ordered the diet advanced to clear liquids and the subject has ingested fluids by mouth without nausea or vomiting.
 
Exclusion Criteria:
 
 1. Has the presence or history of a clinically significant disorder involving the cardiovascular, respiratory, renal, gastrointestinal, immunologic, hematologic, endocrine, or nervous system(s) or psychiatric disease that would contraindicate participation, as determined by the Investigator. 2. Has any clinical laboratory test result outside the accepted range that has been confirmed upon re-examination and deemed to be clinically significant. 3. Has a clinically significant illness or condition any time before dosing with study drug that would contraindicate participation, as determined by the Investigator. 4. Has a life expectancy <8 weeks. 5. For age groups A and B: Has a malabsorption, gastroenterologic, or abdominal condition that would interfere with the absorption of study drug. 6. Has evidence of increased intracranial pressure. 7. Has a respiratory condition requiring intubation or resulting in active bronchiolitis, asthma, stridor, or difficulty breathing due to congestion and increased nasal secretions, including oxygen (O₂) saturation ≤92%. 8. Has a history of seizures. 9. Subject (and/or mother if subject is nursing) has used medications with actions characteristic of monoamine oxidase inhibitors (MAOIs) within 14 days before the start of the study drug is prohibited. Standard daily pediatric multivitamins may be taken until enrollment into the study but will be restricted during the study. 10. Subject (and/or mother if subject is nursing) has received preoperative opioids for more than 72 consecutive hours. 11. Subject (and/or mother if subject is nursing) has received oxycodone or oxymorphone within 48 hours prior to screening. 12. Subject (and/or mother if subject is nursing) has ingested caffeine- or xanthine-containing products (eg, theophylline) within 48 hours before dosing. These products are also prohibited during periods when blood samples are collected. 13. Has a history of relevant drug allergies, food allergies, or both (ie, allergy to oxymorphone or other opioid analgesics) that could interfere with the study. 14. Parent or legal guardian is unable to provide consent for any reason (eg, mental or physical disabilities, language barriers, or is unavailable).

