8. INVESTIGATIONAL PLAN

8.1. Study Design

This is a phase 3, post market study being conducted for Pediatric Research Equity Act (PREA) commitment, with an open-label, single-dose, dose selection phase and a randomized, double-blinded, placebo-controlled multiple-dose phase to characterize the efficacy, safety, tolerability, and PK of oxymorphone HCl in pediatric subjects with acute moderate to severe postoperative pain for whom an opioid may be determined to be an appropriate treatment option. It is a multicenter study conducted at up to 25 sites.

All subjects will be enrolled preoperatively up to 5 days before surgery with the expectation that they will require IV access after surgery and postoperative analgesia with an opiate medication.

[figure not shown]
Four (4) separate age groups of subjects will be enrolled in the study, with recruitment of older infants and toddlers preceding involvement of the youngest age subjects (Figure 1).

The study will consist of a screening period; a post-surgery evaluation; a treatment phase (single-dose open-label phase and placebo-controlled, double-blinded, multiple-dose phase, each occurring after surgery) to evaluate efficacy, safety, tolerability, and PK; an end-of-treatment (EOT) assessment 24 hours after the last dose of study drug; and 2 follow-up contacts (at 3 ± 1 and 14 ± 2 days after the last dose of study drug). The total duration of the study, excluding screening, for subjects in the open-label, dose-selection phase will be approximately 15 days from the first dose of study drug to last follow-up. The total duration of the study, excluding screening, for subjects in the multiple-dose phase will be up to 17 days from the first dose of study drug to last follow-up.

[figure not shown]
For all age groups, the screening period will occur within 5 days before surgery.

Eligible subjects whose parent or guardian provides written consent will have study assessments performed at screening.

Figure 1: Study Design

*Must complete the single-dose phase, AND preceding age group must have completed the multiple-dose phase.

d=Days; IDMC=Independent data monitoring committee; m=Months; PBO=Placebo; SOC=Standard of care; TBD=To be determined; yr=Years

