8.1.1. Screening Phase

The Investigator, or designee, will identify a potential candidate for the EN3319-304 study. The Investigator, or designee, will obtain informed consent per Institutional Review Board (IRB)/ Institutional Ethics Committee (IEC) requirements and will screen the subject at any time within 5 days prior to surgery. Informed consent will be obtained via parent or legal guardian prior to initiation of any study-related procedures. After the informed consent has been signed, and a unique subject number has been assigned, screening assessments/procedures will be completed (see Table 3 and Table 4 Blood samples for baseline clinical laboratory tests as detailed in Table 9 may be collected at any time within 5 days prior to surgery. Clinical labs drawn as part of the standard of care (SOC) (including the intraoperative period) will be acceptable for study purposes provided they are taken prior to first surgical incision and assessed by the Investigator prior to administration of the first dose of study drug (see Table 9 for a list of analytes). Details on selection of subjects will be based on their anticipated need for opioids for management of pain following surgery. The Investigator will explain the study to the subject's parent(s)/legal guardian(s). All screening phase assessments and procedures will be completed according to protocol preferably on the same day as outlined in Table 3 (single-dose phase) and Table 4 (multiple-dose phase).

Screening activities will include:

- Obtaining written informed consent from parent(s)/legal guardian(s) (section 18.3).
- Assessing entry criteria: inclusion/exclusion criteria (section 9.1 and section 9.2) will be assessed during the screening phase.
- Recording demography: gender, age, and race.
- Recording medical/surgical history: all previously existing and current medical conditions including any past surgical procedures. This assessment may be deferred until the preoperative or intraoperative time point.
- Performing physical examination: a comprehensive physical examination, including height and weight, to assess the subject's overall health and physical status. Record only abnormalities observed during the examination. This assessment may be deferred until the preoperative or intraoperative time point.
- Obtaining EKG.
- Measuring vital signs (section 12.8).

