9.3.1. Replacement of Subjects

9.3.1.1. Single-dose Phase

In the single-dose phase, up to 3 dose cohorts of 5 subjects may be studied (doses to be determined by IDMC) for each age group (see Table 7). Enrollment in each cohort will continue until at least 5 evaluable subjects are completed. To be considered an evaluable subject, each subject must meet the following criteria:

1. Receive expected dose of study drug
2. Complete at least 4 hours of post-dose assessments
3. Complete at least 3 PK assessments

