10.2.1. Prohibited Medications

During the study, the following medications are prohibited:

- Preoperative opioids administered for a period of more than 72 hours in duration.
- Any investigational drugs other than oxymorphone HCl immediate-release oral liquid from 30 days prior to screening through EOT.
- Oxycodone or oxymorphone within 48 hours prior to screening.
- Cough syrup containing an opioid from screening through EOT.
- MAOIs from screening through EOT
- Products containing caffeine or xanthine.
- Non-opioid analgesics (acetaminophen and/or NSAIDs) during the Multiple-dose Phase

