14.1.2. Pharmacokinetics

Earlier PK modeling indicated that the best fitting model was 2 compartmental and that the inter- and intra-subject coefficient of variation (CV[%]) for clearance and volume of distribution were 54% and 20%, respectively. If each subject provides 3 data points in the ranges of absorption and terminal elimination phases, the total CV(%) (combination of the inter- and intra-subject CV[%]) is approximately 60%. Based on this assumption, a total of 34 subjects are needed to provide estimates of clearance and volume of distribution if their 95% confidence interval (CI) is within the range of 0.6 to 1.4 of the point estimates with 90% power.

For the single-dose phase, 5 subjects from each age group will receive oxymorphone (up to 60 total subjects, depending on IDMC recommendations for each age group). For the multiple-dose phase, 10 subjects from each age group will be randomized to receive either oxymorphone or placebo (40 total subjects). This will provide up to 80 subjects that are evenly distributed over the 4 age groups for the final population PK modeling and analysis.

PK in this study will be characterized using population PK modeling and analysis. Blood samples collected from the single-dose phase will be based on a 4-hour dosing interval since this is the specified period for evaluation of the dose strength. Four (4) blood samples will be collected from each subject according to the randomized subject number. Subjects with even subject numbers will have blood samples collected at 0.5, 2, 3, and 4 hours after dosing. Subjects with odd subject numbers will have blood samples collected at 1, 2, 3, and 4 hours after dosing. A window of ± 10 minutes is allowed.

In the multiple-dose phase, PK blood samples will be collected just before each dose (ie, at each trough). Population PK analyses will be used to estimate the clearance from multiple trough samples collected in the same subject. The date/time and study drug dose, as well as the date/time of each sample collection, must be recorded accurately. However, no specific schedule needs to be followed other than that each sample be collected as a trough sample just before the next dose.

If any other source of oxymorphone is administered (including oxycodone, which has oxymorphone as a metabolite), no further PK samples will be collected.

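### The 48-hour oxycodone/oxymorphone window ends at screening rather than at first dose, so short exposure before surgery can leave carry-over in the single-dose PK data

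*Protocol*

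**What the plan says.** Exclusion 11 in Protocol 9.2, which matches the synopsis, reads "Subject (and/or mother if subject is nursing) has received oxycodone or oxymorphone within 48 hours prior to screening". The list in Protocol 10.2.1 repeats the anchor: "Oxycodone or oxymorphone within 48 hours prior to screening". SAP 3.6.1 records the same item.

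Protocol 8.1.1 says that the site "will screen the subject at any time within 5 days prior to surgery", and Protocol 8.1 says: "For all age groups, the screening period will occur within 5 days before surgery".

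Protocol 14.1.2 (and the synopsis) treats oxycodone as a source of oxymorphone: "If any other source of oxymorphone is administered (including oxycodone, which has oxymorphone as a metabolite), no further PK samples will be collected". Under Protocol 9.3.1.1, an evaluable single-dose infant must, among other things, "Complete at least 3 PK assessments", and a cohort keeps enrolling until it has at least 5 evaluable infants.

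Other items have other anchors. Exclusion 9 counts MAOI use back from the start of study drug. In 10.2.1, MAOIs and opioid cough syrup are barred from screening to end of treatment. Exclusion 12 (caffeine and xanthines) differs between two places: the synopsis has "eg, theophylline) within 48 hours before dosing", while 9.2 has "eg, theophylline) within 48 prior to screening", with the time unit missing.

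**The concern.** The protocol's own rule on other oxymorphone sources shows why prior exposure matters: it interferes with measuring the study drug. A window meant to protect that measurement should end where measurement begins, at the first dose. Here it ends at screening, and the interval from screening to surgery has no criterion or named prohibition of its own.

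An infant exposed in that interval, directly or through a nursing mother, can meet exclusion 11. Re-confirming eligibility after surgery (8.1.2) does not help, because it re-tests a condition that still refers to screening.

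The data at stake are the single-dose concentrations. Under 8.2.1 the IDMC reviews them, with efficacy and safety data, before recommending the next cohort's dose. Cohorts have 5 infants, so one distorted profile carries weight.

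**Working it through.** The plan states no figure to reproduce. The check is a timeline, followed by a reading of the rules side by side.

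**1. What the window covers.** Inputs: 48 hours (9.2, 10.2.1) and screening 0 to 5 days before surgery (8.1, 8.1.1). With screening s days before surgery, the window runs from 24s + 48 to 24s hours before surgery, leaving the last 24s hours outside it.

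**2. The part that matters.** By the protocol's own standard, 48 hours is enough, so only exposure in the last 48 hours before dosing counts. Let h be the hours from surgery to first dose. The documents do not give h; 0 and 12 are assumptions. Postoperative analgesia for the infant must already be free of both drugs (8.1.2), so the relevant uncovered time is min(24s, 48 − h).

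| Screening day | Window covers (h before surgery) | Outside window (h) | Relevant, h = 0 | Relevant, h = 12 |
|---|---|---|---|---|
| 0 | 48 to 0 | 0 | 0 | 0 |
| −1 | 72 to 24 | 24 | 24 | 24 |
| −2 | 96 to 48 | 48 | 48 | 36 |
| −3 | 120 to 72 | 72 | 48 | 36 |
| −5 | 168 to 120 | 120 | 48 | 36 |

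For a nursing mother the postoperative hours are covered by advice only (10.2), so h is not a firm deduction for her. The ceiling stays at 48 hours.

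**3. Whether carry-over could be material.** The fraction remaining t hours after last intake is 2^(−t/half-life). The documents give no half-life; 4, 8 and 12 hours are assumptions.

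| Hours since last intake | 4 h | 8 h | 12 h |
|---|---|---|---|
| 6 | 35% | 59% | 71% |
| 12 | 12.5% | 35% | 50% |
| 24 | 1.6% | 12.5% | 25% |
| 48 | 0.02% | 1.6% | 6.3% |

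These are fractions of the earlier exposure, not of the study-drug level. The bias also depends on the size of the earlier dose, and for maternal intake on transfer in milk; neither is in the documents.

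**4. What happens to an exposed infant.** It is unclear whether the stop-sampling rule reaches intake before the first dose.

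- If it does not, sampling goes ahead. A pre-dose sample is drawn (8.1.3), but 14.7.1 sets rules only for values below the quantification limit and none for a quantifiable pre-dose level. The populations in 14.2.1 and 14.2.1.1 do not remove the infant. One infant is 1/5 = 20% of a cohort.
- If it does, at most the pre-dose sample exists: 1 is fewer than the required 3. The infant is not evaluable, and enrolment continues under 9.3.1.1.

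These are alternatives. The 20% share belongs only to the first, since in the second the infant is replaced. Multiple-dose subjects are not replaced (9.3.1.2).

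**The case against.** The strongest reply is that the protocol is not silent. Section 10.2 tells sites to avoid drugs with analgesic effect during the study unless the protocol allows them, and this sentence stands before the list of restrictions that begin after surgery. Exclusion 10 removes an infant or nursing mother after more than 72 hours of uninterrupted preoperative opioids. Exclusion 16 gives the investigator discretion, and 9.3 allows discontinuation for use of a prohibited medication. The pre-dose sample could reveal carry-over, and population PK handling is left to a separate plan that is not among these documents.

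Much of this stands, and it rules out three stronger readings that a reader might infer:

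- That nothing restricts these drugs before surgery. The 10.2 sentence does, in general terms.
- That an infant exposed throughout days −4 to −1 qualifies. Four days is 96 hours, beyond the 72 in exclusion 10, so continuous use is ineligible; only shorter or intermittent use passes.
- That the gap is 120 hours, or 2.5 times the intended window. Exposure more than 48 hours before dosing already meets the protocol's own standard.

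The safeguards still do not close the gap. The 10.2 sentence names neither drug, does not clearly reach mothers, and is not an eligibility criterion. Advice to nursing mothers sits in the list that starts after surgery. The physician's pre-dose review (8.1.3) covers intra- and postoperative drugs, and only for their effect on pain assessment. Section 8.1.1 refers preoperative restrictions to Appendix B, which is a recording list starting in the operating room and contains no restrictions.

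**Conclusion.** The anchor is wrong for its purpose. When screening precedes the day of surgery, an infant or nursing mother with short or intermittent oxycodone or oxymorphone exposure in the last 48 hours before dosing can meet every named criterion. The relevant uncovered time is 0 hours with same-day screening, about 24 hours with screening the day before, and at most 48 hours otherwise. This rests on taking the protocol's 48 hours as sufficient. That carry-over could be material rests on the assumed half-lives.

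The consequence is possible, not shown: biased single-dose PK, or, on one reading of the stop-sampling rule, a non-evaluable infant and a replacement. The documents give no frequency and no evidence that it occurred.

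The practical reach is limited. The SAP drops all PK analyses (3.15, 7.10, 8) and reports that nobody entered Groups C or D (3.1.1), so a newborn in Group D nursed by a mother taking oxycodone is hypothetical in this study. What remains is mainly the PK that the IDMC used for dose selection in Groups A and B. The conflict between the two versions of exclusion 12 is certain and needs reconciling in any case.

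**What to change.** - Reconcile exclusion 11 in the synopsis and 9.2 with 10.2.1, so that the stated 48 hours are counted back from the first dose of study drug, as the MAOI criterion already is. Apply it to non-study oxycodone and oxymorphone, in infant and nursing mother. A ban on the two drugs running to end of treatment with no such qualifier would catch the study drug itself. No different window length is proposed.
- Check it at the existing post-surgery eligibility re-confirmation (8.1.2), with a question on maternal intake.
- Give exclusion 12 one anchor, and supply the missing unit in 9.2.
- State whether the stop-sampling rule covers intake before the first dose.
- State that infants with recorded non-study oxycodone or oxymorphone in the window, or a quantifiable oxymorphone level before the first dose, are flagged and left out of the non-compartmental PK summaries and of the PK data given to the IDMC. They stay in the nurse-controlled analgesia endpoint. The pre-dose assay can serve this purpose but not eligibility, because samples are analysed in cohort batches (13.1.3).
- Leave SAP 3.6.1 alone; it records what was prohibited in a study that has ended.

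Cost: wording changes, a few infants failing the re-check after consent, and one added question, because the protocol does not describe recording the mother's medications.

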9.3. Subject Discontinuation Criteria

A premature discontinuation will occur when a subject ceases participation in the study, regardless of circumstances, prior to the completion of the protocol. Subjects can be prematurely discontinued from the study for one of the following reasons:

- An AE
- Lack of efficacy
- Use of an opioid antagonist (eg, naloxone)
- A protocol violation (reason must be specified, for example: lack of compliance, use of a prohibited concomitant medication, failure to meet inclusion/exclusion criteria after study entry, etc.)
- Withdrawal by subject (reason must be specified)
- The subject was “lost to follow-up”
- Unblinding of a subject based on medical need
- Sponsor decision to terminate trial
- Investigator decision

Other Reasons (reason must be specified)

If a subject discontinues from the study, all EOT procedures should be conducted as detailed in section 3. The date a subject discontinues the treatment and the reason for discontinuation will be recorded in the source documentation and electronic Case Report Form (eCRF). If, however, a subject withdraws consent, no EOT procedures are required except for the collection of AE information. This information should be recorded in the source documentation and the eCRF.

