8.1.7. End-of-treatment/Early Termination

At the completion of the single- or multiple-dose phases, EOT assessments and procedures will occur at 24 hours after the last study drug administration or upon early study withdrawal. Each subject will be required to complete all EOT/ET assessments and procedures unless consent has been withdrawn. EOT assessments will include:

- Ongoing collection of AEs/SAEs (section 12).

- Performing physical examination: a brief physical examination, excluding length and weight, to assess the subject's overall health and physical status.
- Measuring vital sign (section 12.8).
- For the single-dose phase, collecting a blood sample for PK assessments (at 24 hours or upon EOT, if possible).
- For multi-dose phase, no blood sample for PK assessments will be drawn at EOT.
- Obtaining clinical laboratory tests (section 12.7): clinical laboratory tests as part of SOC will be acceptable.
- Assessing respiratory and neurological function (section 12.10, section 12.11 and Appendix A).
- Telemetry and pulse oximetry will be ongoing to EOT or ET.
- Updating and recording concomitant medications (including NCA rescue medications).
- Pain assessment (FLACC or NIPS; Appendix C or Appendix D, respectively) will be recorded.
- Recording of food consumption from the period 1 hour prior to administration of study drug through EOT assessment; record all times that any food was consumed and what food was consumed (DAT, DAT-soft, FF, CF, water, formula, breast milk).
- Converting subjects to a marketed opioid upon discharge, if required.
- Scheduling the 3-day and 14-day follow-up telephone call: assessment to include ongoing or new AEs, SAEs, and associated concomitant medications. The complete Schedule of Events is provided in Table 3 and Table 4

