9.3.1.2. Multiple-dose Phase

In the multiple-dose phase, a single dose cohort (dose to be determined by IDMC) will be studied for each age group (see Table 8). Subjects will not be replaced in the double-blind multiple-dose phase.

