10.1.5. Follow-up

A documented follow-up telephone call will be required 3 days and 14 days after the last dose of study drug. Site staff will collect information regarding new AEs (including SAEs) or resolution of ongoing AEs/SAEs, including concomitant medications being used to treat any SAE or ongoing AE and any new analgesic medications started after EOT or ET.

The date of EOT or ET from the study will be recorded by the Investigator (or assigned designee) and will be the official EOT/ET for each subject. Subjects may take analgesics (opioid or non-opioids) according to SOC after EOT. Study participation will end with the completion of the 14-day follow-up telephone call.

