11. ASSESSMENT OF EFFICACY

11.1. Primary Efficacy Measurements

11.1.1. Morphine Consumption via NCA

NCA is an established form of postoperative analgesia, similar in nature to other demand-led analgesic regimens (eg, PCA), but tailored for patients who are too young or unable to use PCA.(14-18). The primary efficacy variable will be the cumulative total amount of morphine required for analgesia (including background infusion and boluses).

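### Section 9.3 recognises only leaving the study, so a multiple-dose infant who stops early can carry a shortened morphine total into a primary endpoint with no fixed window and no rule for it

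*Protocol*

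**What the plan says.** - **Discontinuation (Protocol 9.3).** "A premature discontinuation will occur when a subject ceases participation in the study, regardless of circumstances, prior to the completion of the protocol". The list of reasons opens with "Subjects can be prematurely discontinued from the study for one of the following reasons" and includes an adverse event, lack of efficacy and use of an opioid antagonist. The section's only reference to stopping treatment is administrative: "The date a subject discontinues the treatment and the reason for discontinuation will be recorded in the source documentation". It does not ask for further morphine recording.
- **End of treatment (Protocol 8.1.7).** "EOT assessments and procedures will occur at 24 hours after the last study drug administration or upon early study withdrawal".
- **After exit (Protocol 10.1.5).** "Subjects may take analgesics (opioid or non-opioids) according to SOC after EOT". The follow-up calls ask about drugs used for adverse events and "any new analgesic medications started after EOT or ET".
- **Analysis set (Protocol 14.2.1.2 and 9.3.1.2).** Intent-to-treat needs one dose and one later pain score. "Subjects will not be replaced in the double-blind multiple-dose phase".
- **Primary endpoint (Protocol 11.1.1).** "The primary efficacy variable will be the cumulative total amount of morphine required for analgesia (including background infusion and boluses"). No end time is given.
- **Analysis (Protocol 14.5 to 14.5.3).** A mixed model with a random subject effect and fixed effects for treatment and age group. There is no time term, and no imputation, scaling or ranking rule for an incomplete total.
- **SAP 3.4, 7.6 and 8.** All efficacy analyses are dropped after early termination. SAP 7.7 keeps a descriptive summary of total morphine and its duration of use.

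**The concern.** A lower total counts as better analgesia. A running sum has a natural failure: it stops growing when observation stops. Some listed reasons for stopping are themselves outcomes, such as poor pain control, adverse events and reversal of opioid effect. The length of the record can therefore depend on how the infant fared and on the arm.

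With 20 infants per arm and no replacement, two or four shortened totals are enough to move the comparison. Exits for lack of efficacy, plausibly more frequent on placebo, would lower the placebo mean and hide an effect. Exits for adverse events or antagonist use on oxymorphone would lower the active mean and mimic one. Neither shift reflects analgesia.

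**Working it through.** **1. The plan's own figure.** Protocol 14.1.1 gives effect size 0.9, two-sided alpha 0.05, 80% power and 20 per group. By the normal formula, n = 2 × (1.96 + 0.842)² / 0.9² = 19.4, so 20 per arm. Power at 20 per arm is 0.812 (normal) or 0.792 (t-test, 38 df). The figure reproduces. It makes no allowance for shortened totals.

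**2. When a leaver scores lower.** Let the leaver use morphine at rate r_L until time t, and the completer at rate r_C over window W. The totals are r_L × t and r_C × W, so the leaver is lower when r_L / r_C < W / t.

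Using Table 6 (Protocol 8.1.4) for Groups A and B, with an assumed W of 24 h:

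| Leaver's rate (mcg/kg/h) | Exit | Total (mcg/kg) | Below completers averaging more than |
|---|---|---|---|
| 5 + 3 × 10 = 35 | 6 h | 210 | 210/24 = 8.75 mcg/kg/h |
| 30 + 3 × 15 = 75 (table maximum) | 6 h | 450 | 450/24 = 18.75 mcg/kg/h |
| 35 | 18 h | 630 | 630/24 = 26.25 mcg/kg/h |

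Early exit can make a heavy user look light. Late exit need not.

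**3. Effect on power.** The documents give no withdrawal rate, exit time, mean or SD, so all of these are assumptions: 20 per arm; 24 h totals normal with placebo mean 500 and SD 180; active mean 500 − 0.9 × 180 = 338; linear accrual; the highest placebo users leave; and each leaver's total is multiplied by exit time/24. Simulated power of the two-sided t-test:

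| Placebo leaving | Exit at 8 h (× 8/24) | Exit at 16 h (× 16/24) |
|---|---|---|
| none | 0.79 | 0.79 |
| 2 of 20 (10%) | 0.51 | 0.70 |
| 4 of 20 (20%) | 0.22 | 0.59 |

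If leavers at 8 h are random instead, power is about 0.56 and 0.29. The mean-to-SD ratio also matters. With the highest users leaving halfway, power for two and four leavers is 0.61 and 0.38 at a placebo mean of 3 SD, and 0.66 and 0.51 at 2 SD.

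**4. The opposite direction.** Assume no true difference, means of 3 SD, and 4 of 20 active infants leaving at random. The two-sided false-positive rate rises from 5% to about 12% (exit halfway) or 19% (exit at a quarter of the window), almost all of it favouring oxymorphone.

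**5. The window for completers.** The synopsis gives treatment of up to 24 hours, and Protocol 10.2 refers to a 24-hour assessment period. Section 8.1.7 puts end of treatment 24 h after the last dose. With at least three doses at least 4 h apart and the last by 18 h (Protocol 8.1.6), the last dose falls at 8 to 18 h. End of treatment is then 8 + 24 = 32 h to 18 + 24 = 42 h after the first dose. The accumulation period is therefore unsettled even without withdrawals.

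**The case against.** - **Scoring on the partial total is not written anywhere.** This is correct: section 14.5 is silent. The random subject effect and the planned curves over time could suggest repeated measurements, with later values missing rather than frozen. But the model has no time term, so even on that reading a leaver would contribute only early, and hence low, cumulative values.
- **Exit is not compulsory.** This also stands. Section 9.3 says subjects can be discontinued, and inadequate relief is first met by boluses and background increases, which add to the endpoint. Much poor efficacy would show as higher morphine, as intended. The documents give no basis for expecting frequent exits.
- **Medication recording does not stop at exit.** A reader of 10.1.5 alone might infer that morphine after exit is lost. The documents do not support that. Table 4 (footnote n) and SAP 3.6 carry concomitant medication to 14 days after the last dose, and Appendix B asks for every medication after dosing. Section 10.1.5 and the main recording sentence of 10.2 (up to 24 hours after the first dose) are narrower. Capture is inconsistent rather than absent. What remains is that no passage adds opioid given after exit to the endpoint.
- **No biased test will be run.** The SAP removes efficacy. This limits the practical consequence to the descriptive morphine summary.

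**Conclusion.** The gap is real in the protocol's planned primary analysis: outcome-related exit, retention in intent-to-treat, and a cumulative endpoint with neither a window nor a rule for short records. The bias can run either way.

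Its size depends on when and how often infants leave. In the illustration, power ranges from 0.70 down to 0.22 for 10% to 20% of placebo infants leaving at 16 h or 8 h. This rests on the assumed mean, SD, linear accrual and departure of the highest users, and on partial totals being analysed unadjusted.

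A reader might go further and conclude that every infant stopping for lack of efficacy is scored as a low user. That does not follow. The scoring rule is inferred from silence, exit is permitted rather than required, and the ranking turns on exit time relative to rate of use. Because no efficacy analysis will be run, the point ranks below a must-fix.

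**What to change.** 1. **Protocol 9.3:** define stopping study drug and leaving the study as separate events, each with its own date and reason. This changes what is recorded, not who stops or what care follows.
2. **Recording:** for infants who stop drug but whose consent stands, record all morphine (background and bolus) and any substituted opioid to one fixed time after the first dose. Reconcile that time with the 24-hour period in the synopsis and 10.2 and with end of treatment in 8.1.7. Align the medication-capture wording in Table 4, Appendix B, 10.1.5 and 10.2.
3. **Protocol 11.1.1 and 14.5.1:** define the endpoint as cumulative morphine from first dose to that time, whether or not study drug was stopped. State how substituted opioid is handled.
4. **Sensitivity analysis:** for records that still end early for lack of efficacy, add a rank-based analysis that places those infants at the worst rank.
5. **Abbreviated report:** show observation time and exit status beside each morphine total. The duration in SAP Table 8 is last minus first morphine dose, which is not time observed.

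The cost is wording and extra chart abstraction. Inclusion criterion 7 already expects a 24-hour inpatient stay after dosing. No added procedures or infants are needed.
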